### **Intent-to-Treat Influenza-Infected Patient Set**

The ITTi set is a subset of ITT patients who have had a laboratory confirmation of influenza infection (polymerase chain reaction [PCR] result) from any swab sample collected at baseline or during the study. The ITTi set is the main efficacy set, unless specified otherwise.

Decisions on patient exclusion from the ITTi set will be made prior to database lock. Excluded patients will be documented, together with the reason for exclusion.

### **Pharmacokinetic-Evaluable Set**

The pharmacokinetic-evaluable patient (PKEP) set comprises all patients in the ITT set who have at least one post-dose drug concentration measurement at a scheduled visit time-point. Patients may be excluded from the PKEP set if they significantly violate the inclusion or exclusion criteria or deviate significantly from the protocol, or if data are unavailable or incomplete (which may influence the PK analysis), such as the absence of properly documented date and time for the baloxavir marboxil administration and PK sample collection.

Decisions on patient exclusion from the PKEP set will be made prior to database lock by the clinical pharmacologist. Excluded patients will be documented, together with the reason for exclusion.

### **Safety Set**

The safety set will be the same as the ITT set (i.e., patients who have received any portion of a single dose) regardless of whether or not they had any follow-up visits.

## **4. STATISTICAL ANALYSES**

The number of patients who enroll, discontinue, or complete the study and the number of patients who discontinue, or complete study treatment will be summarized. Reasons for premature study withdrawal and study treatment discontinuation will be listed and summarized. Major protocol deviations will be listed and summarized and evaluated for their potential effects on the interpretation of study results. A summary of enrollment by country and investigator name will be provided. Exclusion of patients from the analysis sets will be summarized, including the reason for exclusion.

### **4.1 GENERAL CONSIDERATIONS**

Disposition summaries will be based on the 'All Patients' set. Analysis of safety data will be based on the safety set and analysis of PK data will be based on the PKEP set.

The analysis set for efficacy and virology will be the ITTi set. Analysis of palatability will be based on those patients in the ITT set who consented to Version 2 (or subsequent versions) of the Study CP40559 protocol.

In safety analyses, all deaths are included, from all sources, regardless of whether a complete death date is available; patients who died with only a partial death date available will be included.

Partial dates for AEs, concomitant medications, laboratory assessments, and medical history will be imputed following a conservative approach.

### **Visit Windows**

[Table 2](#) presents the acceptable time windows for parameters other than data from the patient diary and PK assessments.

**Table 2 Acceptable Time Windows for Parameters other than Data from the Patient Diary and PK Assessments**

Time Point (Scheduled Time point)	Acceptable Time Window
Pre-dose at Visit 1 (Day 1) a	Before dosing on Day 1
Post-dose at Visit 1 (Day 1) a	After dosing on Day 1
Visit 2 (Day 2)	Day 2
Optional Visit 1 (Day 3)	Day 3
Visit 3 (Day 4)	Between Day 4 and Day 5
Visit 4 (Day 6)	Between Day 6 and Day 7
Visit 5 (Day 10)	Between Day 8 and Day 12 as follows: If a patient presents between Day 8 and Day 11 and presents on Day 12 then the visit between Day 8 and Day 11 will be classed as Visit 5 and the Day 12 visit will be classed as Optional Visit 2 If a patient does not present between Day 8 and Day 11 and presents on Day 12 this will be classed as Visit 5
Optional Visit 2 (Day 15)	Between Day 12 and Day 22
Visit 6 (Day 29)	On or after Day 23

a If time is missing for data collected on Visit 1 where this data should be collected at 'v1 screening' or 'v1 post-dose' as per the schedule of activities, then it is defined as 'Pre-dose at Visit 1 (Day 1)' or 'Post-dose at Visit 1 (Day 1)', respectively.

Measurements collected within the acceptable time window for each scheduled assessment time point, including data obtained at the time of withdrawal, will be used for the analyses of all endpoints at each assessment time point. For all patients with multiple values within a visit window, the value obtained closest to the target time point will be used. If two measurements collected with the same time deviation exist before and after the target time point, the measurement obtained before the target time point will be adopted for analysis. The assessment time point having no measurements within the corresponding acceptable time window will be considered as missing.

In the assessment of data from sources other than the patient diary, if there are multiple values which may be adopted for a scheduled assessment time point (even though the above rules have been strictly followed), the measurements at the time point entered in the Case Report Form (CRF) will be adopted.

For summaries of data not collected by visit, such as AEs, medical history and concomitant medications, all data up to the study completion/discontinuation date will be included.

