5.3.1 Adverse Event Reporting Period

Investigators will seek information on adverse events at each patient contact. All adverse events, whether reported by the parent/caregiver or noted by study personnel, will be recorded in the patient's medical record and on the Adverse Event eCRF.

After informed consent has been obtained but prior to initiation of study drug, only serious adverse events caused by a protocol-mandated intervention (e.g., invasive procedures such as biopsies, discontinuation of medications) should be reported (see Section 5.4.2 for instructions for reporting serious adverse events).

After initiation of study drug, all adverse events will be reported until 28-days after the last dose of study drug.

Instructions for reporting adverse events that occur after the adverse event reporting period are provided in Section 5.6.

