5.4.2.2 Events That Occur after Study Drug Initiation

After initiation of study drug, serious adverse events and adverse events of special interest will be reported until 28 days after the last dose of study drug. Investigators should record all case details that can be gathered immediately (i.e., within 24 hours after learning of the event) on the Adverse Event eCRF and submit the report via the electronic data capture (EDC) system. A report will be generated and sent to Roche Safety Risk Management by the EDC system.

In the event that the EDC system is unavailable, the paper Clinical Trial Serious Adverse Event/*Special Situations Form* provided to investigators should be completed and submitted to the Sponsor or its designee immediately (i.e., no more than 24 hours after learning of the event), either by faxing or by scanning and emailing the form using the fax number or email address provided to investigators. Once the EDC system is available, all information will need to be entered and submitted via the EDC system.

Instructions for reporting serious adverse events that occur >28 days after the last dose of study treatment are provided in Section [5.6](#).

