### **1.2.3 Analysis Timing**

The primary study analysis will occur when the last patient has either withdrawn from the study or completed his or her Day 29 visit and will be based on all available data for all patients up to and including their Day 29 assessment, as well as safety follow-up data for patients that withdrew from the study prior to Day 29.

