#### **4.2.1.1 Adverse Events**

AEs will be classified by system organ class (SOC) and preferred term (PT) using the latest version of the Medical Dictionary for Regulatory Activities (MedDRA) at the time of database lock and AE severity will be graded according to National Cancer Institute Common Terminology Criteria for Adverse Events (NCI CTCAE) Version 5.0 or the Adverse Event Severity Grading Scale for events not specifically listed in NCI CTCAE toxicity grading scale (Table 2 of the Protocol) on the electronic CRF. AEs reported after the initial dose of the study drug will be used for safety analyses.

In summaries by SOC and PT, AEs will be sorted by overall decreasing frequency within each SOC and PT.

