#### **All Adverse Events**

Only treatment-emergent AEs will be summarized. Treatment-emergent events are defined as those AEs with observed or imputed onset date on or after the start date of trial treatment. Only where the most extreme intensity is greater than the initial intensity (or if most extreme intensity is not missing and initial intensity is missing) will events with an onset date prior to the start of study treatment be considered treatment-emergent. An AE with a completely missing start date will be assumed to be treatment-emergent unless the AE has a complete non-imputed end date that is prior to study Day 1.

AEs will be coded and tabulated by SOC and/or PT. In tabulations, PTs and their associated SOC will be presented in order of descending frequency. AEs will also be tabulated by severity and relationship to the study drug as indicated by the investigator.

A listing of all AEs will be produced, and the following will be summarized:

- All AEs
- Serious AEs
- AEs related to study medication
- AEs by severity
- AEs by outcome

- AEs by onset (Day 1–7, Day 8–14, and Day  $\geq$ 15)
- AEs leading to withdrawal from study
- AEs leading to withdrawal from study drug
- AEs leading to death
- AEs leading to a dose modification or interruption
- Most frequent AEs

A listing of incorrect doses and overdoses will be provided if they occur during the study and a listing of any accidental overdose or medication error AEs will also be provided.

If there are sufficient number of patients that are  $\leq$ 27 days old, then summaries of AEs split by age ( $\leq$ 27 days and  $>$ 27 days) will be produced where required.

If the overall number of AEs is low then listings may be provided instead of the above summaries.

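### SAP 4.1 ends the adverse event summaries at each infant's completion or discontinuation date, which conflicts with SAP 1.2.3 and with the protocol's 28-day reporting period

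*SAP*

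**What the plan says.** Four sets of statements bear on which adverse events enter the summaries.

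- **SAP 4.1, Visit Windows, after Table 2.** For data not collected by visit, with adverse events named as an example alongside medical history and concomitant medications, "all data up to the study completion/discontinuation date will be included".
- **SAP 1.2.3.** The primary analysis is "based on all available data for all patients up to and including their Day 29 assessment". The same sentence then adds a second source, for infants who leave early: "as well as safety follow-up data for patients that withdrew from the study prior to Day 29".
- **SAP 4.1 (opening text) and 4.2.1.1.** On deaths, SAP 4.1 is explicit: "In safety analyses, all deaths are included, from all sources, regardless of whether a complete death date is available". On adverse events in general, SAP 4.2.1.1 says: "AEs reported after the initial dose of the study drug will be used for safety analyses". Its definition of treatment emergence has a lower bound only: "Treatment-emergent events are defined as those AEs with observed or imputed onset date on or after the start date of trial treatment". Neither of the last two sentences gives an end date. SAP 4.2.1.1 also plans a listing of every adverse event and a presentation of every event of special interest.
- **Protocol 5.3.1 and 5.4.2.2.** The first section covers all events: "After initiation of study drug, all adverse events will be reported until 28-days after the last dose of study drug". The second sets the same period for the immediately reportable ones: "serious adverse events and adverse events of special interest will be reported until 28 days after the last dose of study drug". Neither section makes an exception for infants who have left the study.

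**The concern.** Safety is the primary objective, and its endpoint is the incidence, severity and timing of events. The protocol tells sites to report events for 28 days after dosing. SAP 1.2.3 says that safety data on withdrawn infants will be used. The sentence in SAP 4.1 gives a different end point, one that depends on when each infant left.

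A programmer who follows that sentence would drop from the summaries an event that the site was obliged to report. Suppose an infant is withdrawn on Day 5 and admitted to hospital on Day 12. That is a reportable serious event inside the 28-day period. It would be listed but not counted in the summaries of all events, serious events, severity or onset. SAP 4.3.1 takes influenza-related complications from the adverse event pages, so the same event could also be missing from that secondary endpoint.

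**Working it through.** **Step 1. The plan's own day count.** Protocol 3.1 gives a 1-day treatment period and a 28-day follow-up: 1 + 28 = 29 days, the stated duration per patient. With one dose on Day 1, 28 days after dosing is Day 29. The sample size of about 30 rests on no formal calculation, so there is no power figure to reproduce.

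**Step 2. Days excluded if SAP 4.1 is applied literally.** Days excluded = 29 − last study day; share = days excluded / 28.

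| Last study day | Days excluded | Share of 28 days |
|---|---|---|
| 2 | 27 | 96.4% |
| 5 | 24 | 85.7% |
| 10 | 19 | 67.9% |
| 15 | 14 | 50.0% |
| 26 (earliest compliant final visit, Day 29 ± 3, Protocol 4.6.1) | 3 | 10.7% |

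These are shares of calendar days, not of events.

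**Step 3. Numerator and denominator.** SAP 3 keeps every treated infant in the safety set regardless of follow-up. A withdrawn infant therefore stays in the denominator while later events leave the numerator. Within the 28 days the rule can only lower a count. One omitted infant out of 30 is 1/30 = 3.3 percentage points.

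**Step 4. Timing.** SAP 4.2.1.1 groups onset into Days 1–7, Days 8–14 and Day 15 onward. An infant withdrawn on Day 5 could contribute nothing to the last two groups under the literal rule.

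**Step 5. Illustration of size (assumptions, not plan figures).** Assume a constant hazard and a 28-day incidence p of any adverse event of 34.6% (37 of 107 in the Japanese pediatric study, Protocol 1.2.4). The range runs from 20.7% (the baloxavir arm in Protocol 1.2.3) to an assumed 60%. Then h = −ln(1 − p)/28, and for an infant leaving on Day 10 the chance that the first event falls in the excluded period is exp(−9h) − exp(−28h).

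- p = 34.6%: 21.8%
- p = 20.7%: 13.5%
- p = 60%: 34.5%

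If 3 of 30 infants left on Day 10, the expected number with a first event excluded would be 3 × 0.218 = 0.66 (range 0.41 to 1.03). That is 0.66/30 = 2.2 percentage points (1.4 to 3.4). This supposes that every such event becomes known to the site, so it is a ceiling for that scenario.

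**Step 6. Which sections settle the matter?** SAP 1.2.3 sets the scope of the primary analysis and includes data on withdrawn infants. SAP 4.1 names adverse event summaries and gives an end date. SAP 4.2.1.1 is silent on an end date, so it neither supports the cut-off nor overrides it. The conflict cannot be resolved from the text.

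**Step 7. Concomitant medications.** Protocol 4.4 defines concomitant therapy as running to the completion or discontinuation visit. For medications, SAP 4.1 matches the protocol.

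**The case against.** The best defence is that the SAP 4.1 sentence is one of inclusion. It closes the visit-window text and can be read as saying only that non-visit data are not windowed. It does not say that later events are excluded. SAP 1.2.3 brings in the data on withdrawn infants, and SAP 4.2.1.1 puts no upper limit on the events used. All deaths are included, all events of special interest are presented and all adverse events are listed, so nothing recorded is hidden. The study is single-arm and descriptive, and an internal committee reviews aggregate safety data. Few events may come to light after withdrawal: Protocol 5.5.1 lets follow-up of an event stop when consent is withdrawn, and no visit is scheduled after early termination.

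Much of this stands. The loss is not settled, the listing keeps events visible, and the number at risk is unknown. But the sentence names adverse events and attaches an end date, and a section that is silent on an end date does not cancel it. A listing does not feed the reported percentages. Post-withdrawal data can exist: Protocol 4.6.2 gives reasons for withdrawal other than withdrawn consent, such as site closure or non-compliance, and asks for every effort to obtain information on withdrawn infants.

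**Conclusion.** The SAP contradicts itself on the data scope of its primary safety summaries, and one of its two rules does not match the protocol's reporting period. Under the literal SAP 4.1 rule, non-fatal events reported after withdrawal and by Day 29 would be missing from the summaries. The exposure can be most of the 28 days for an early leaver, and each omitted infant is 3.3 percentage points at 30 infants. The expected effect depends on a dropout rate that the documents do not give and on how many such events become known.

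A reader might infer more than the documents support:

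- **That the events are certain to be lost.** SAP 1.2.3 points the other way.
- **That only deaths escape the cut-off.** The listing covers all adverse events, and all events of special interest are presented.
- **That early leavers have more events, so incidence is strongly biased.** No document shows this. What follows is only that the cut-off cannot raise a count within the 28 days.
- **That one event would move Cohort III by a third.** The SAP plans no adverse event table by cohort, only a split at 27 days of age if numbers suffice.
- **That completers lose much.** A Day 26 final visit leaves at most 3 days and no later scheduled contact, so that gap comes mainly from the visit window.
- **That the medication and antibiotic summaries are wrong too.** Their cut-off agrees with Protocol 4.4.

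**What to change.** In SAP 4.1, separate adverse events from the other non-visit data. State that summaries of adverse events, serious adverse events and events of special interest, and the influenza-related complications taken from the adverse event pages, include every event with onset from dosing through at least 28 days after dosing (Day 29), regardless of completion or discontinuation date. Where the final visit falls on Days 30 to 32, events collected up to that visit should stay in the summaries; moving them to a listing would remove collected safety data. Add a cross-reference so that SAP 1.2.3 and SAP 4.1 state the same scope. Leave the concomitant medication cut-off unchanged.

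The cost is one SAP sentence and one programming flag, best settled before database lock. No additional data collection is needed, since the protocol already requires these events to be reported. Reported incidence may be slightly higher. The change will not recover events that no one reported after an infant left or after an early final visit.

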## **4.2 PRIMARY ENDPOINT ANALYSES**

### **4.2.1 Safety Endpoints**

The primary objective of this study is to evaluate the safety of baloxavir marboxil in pediatric patients from birth to <1 year with influenza-like symptoms. The safety set will be used for all safety analyses. There will be no formal statistical hypothesis testing. The statistical analyses of safety will be descriptive.

The safety of baloxavir marboxil will be evaluated based on AEs, vital sign measurements (including parent/caregiver recorded temperature), and clinical laboratory tests. Safety parameters will be summarized or listed for the safety set.

#### **4.2.1.1 Adverse Events**

AEs will be classified by system organ class (SOC) and preferred term (PT) using the latest version of the Medical Dictionary for Regulatory Activities (MedDRA) at the time of database lock and AE severity will be graded according to National Cancer Institute Common Terminology Criteria for Adverse Events (NCI CTCAE) Version 5.0 or the Adverse Event Severity Grading Scale for events not specifically listed in NCI CTCAE toxicity grading scale (Table 2 of the Protocol) on the electronic CRF. AEs reported after the initial dose of the study drug will be used for safety analyses.

In summaries by SOC and PT, AEs will be sorted by overall decreasing frequency within each SOC and PT.

#### **All Adverse Events**

Only treatment-emergent AEs will be summarized. Treatment-emergent events are defined as those AEs with observed or imputed onset date on or after the start date of trial treatment. Only where the most extreme intensity is greater than the initial intensity (or if most extreme intensity is not missing and initial intensity is missing) will events with an onset date prior to the start of study treatment be considered treatment-emergent. An AE with a completely missing start date will be assumed to be treatment-emergent unless the AE has a complete non-imputed end date that is prior to study Day 1.

AEs will be coded and tabulated by SOC and/or PT. In tabulations, PTs and their associated SOC will be presented in order of descending frequency. AEs will also be tabulated by severity and relationship to the study drug as indicated by the investigator.

A listing of all AEs will be produced, and the following will be summarized:

- All AEs
- Serious AEs
- AEs related to study medication
- AEs by severity
- AEs by outcome

- AEs by onset (Day 1–7, Day 8–14, and Day  $\geq$ 15)
- AEs leading to withdrawal from study
- AEs leading to withdrawal from study drug
- AEs leading to death
- AEs leading to a dose modification or interruption
- Most frequent AEs

A listing of incorrect doses and overdoses will be provided if they occur during the study and a listing of any accidental overdose or medication error AEs will also be provided.

If there are sufficient number of patients that are  $\leq$ 27 days old, then summaries of AEs split by age ( $\leq$ 27 days and  $>$ 27 days) will be produced where required.

If the overall number of AEs is low then listings may be provided instead of the above summaries.

### **Adverse Events of Special Interest**

All adverse events of special interest (AESI) will be presented. AESI include:

- Cases of potential drug-induced liver injury that include an elevated alanine aminotransferase (ALT) or aspartate aminotransferase (AST) in combination with either an elevated bilirubin or clinical jaundice, as defined in the protocol
- Suspected transmission of an infectious agent by the study drug

#### **4.2.1.2 Deaths**

Details of any deaths will be presented in an individual patient listing.

#### **4.2.1.3 Laboratory Data**

For each of the hematological and biochemical test parameters, summary statistics of observed and change from baseline values at each time point will be presented for each scheduled time point. For laboratory parameters, post-dose observations on Day 1 will be classed as baseline.

Each observed value will be classified into three categories: Normal (for values within the normal range), High (for values higher than normal) and Low (for values lower than normal). The frequency of each category will be summarized for each scheduled time point. Patients with values outside the reference will be listed, with an indication of the direction of the abnormality (High, Low). Additionally, a shift table will present the changes from baseline at each scheduled time point. Additional visual presentations may be produced based on the data accumulated during the study.

A summary of categorized liver lab data and a summary of Grade 1 to 4 of chemistry and hematology data over time (per NCI CTCAE v5.0) will be provided, if there is sufficient data available.

An evaluation of Drug Induced Serious Hepatotoxicity (eDISH) plot will be produced with the patients in each International Council for Harmonisation (ICH) age category indicated by different symbols (Merz et al. 2014).

The number and proportion of patients who meet the pre-specified criteria, shown in [Table 3](#), will be presented during the study.

